4.2.2.2.1 Interviewers

Ventana will secure a site of operation in Port Colborne and recruit and train supervisors and nurse interviewers to administer the questionnaire. None of the staff will be from Port Colborne, nor will they have any affiliation with anyone who lives in Port Colborne. The reasons for this are: i) all residents are potential survey respondents, ii) the sensitive nature of the inquiry, and iii) the need for respondents to feel secure regarding maintenance of the confidentiality of the information that they provide. All interviewers will be qualified nurses who are trained to administer this questionnaire. They will also be certified through an inter-rater reliability testing procedure known as the Objective Structured Clinical Exam (OSCE), which will be described below.

4.2.2.2.2 Quality assurance/Control

In addition to the pre-testing of the questionnaire and along with interviewer training and certification, quality checks will be in place throughout the administration of the interviews. Interviewers will not be able to erase or correct any response by scribbling or covering over, but will be asked to clearly cross out the response and indicate the revision. Questionnaires will also be checked immediately after completion by a site coordinator to identify any problems. Any items that are unclear will be addressed with the interviewer, including the assessment of missing data. The interviewers will get feedback on a regular basis with respect to their performance. In addition, interviews will be periodically monitored for quality control, if the interviewee grants permission.

4.2.2.2.2.1 Inter-Rater reliability

The Objective Structured Clinical Exam (OSCE) approach will be used to assess and certify the competence of 24 survey interviewers at the completion of their training.

The Objective Structured Clinical Examination is a performance-based assessment approach, introduced by Harden et al. in 1975, used extensively in medical and allied health education and the certification and licensing of professionals in these professions. Briefly, this approach uses short standardized and focused encounters between candidates and patients/clients, where candidates' performances are rated by 'expert' examiners guided by checklists and where total test scores are an aggregation of the results of the individual cases. The achievement of both valid and reliable results are facilitated by

using a number of patients/clients and examiners in such an assessment, standardizing the clinical presentations for all candidates, and using checklists to limit examiner subjectivity. The approach has been enhanced by developments in the training and use of "standardized" (simulated) patients/clients. Early studies demonstrated that test results reflecting comprehensive views of performance generally satisfied traditional psychometric criteria. Results of studies where specific components of performance were addressed, e.g. communication skills, interviewing skills, proficiency in English, also produced positive results (Hodges et al., 1996; Rothman & Cusimano, 2000; Rothman & Cusimano, 2001).

4.2.3 Medical tests

As mentioned, the medical tests that will be included in this study include 1) the General Medical Laboratory Screen Tests, 2) the Metal Tests and 3) Non-Specimen Related Tests and Data Points. All procedures will be carried out by a number of trained study nurses at the central study facility.

4.2.3.1 General medical laboratory screen tests

Under the supervision of a trained study nurse, subjects will provide blood and spot urine samples at the central study facility for the General Medical Laboratory Screen Tests. Samples will be stored at the central facility and prepared daily for transport to the central analysis laboratory. At the central analysis laboratory, samples will be sorted and prepared for analysis. Measures from the following general categories will be assessed: haematology, biochemistry and urinalysis. Please see Appendix 11.4 for additional

information regarding methodology, specimen volumes, specimen transport conditions, and reference values for each of the individual tests. Samples will be stored at the central analysis laboratory until such time as the data has been validated. All collection, storage, transport and analysis of samples will be carried out in strict accordance with applicable SOPs.

4.2.3.2 Metal tests

The Metal Tests will require subjects to provide blood at the central study facility under the supervision of a trained study nurse and 24-hour urine sample. The 24-hour urine sample collection procedure is described within Appendix 11.3. Samples will be stored at the central facility and prepared for daily transport to a metals analysis laboratory. This metals analysis laboratory will be responsible for sample sorting and analysis of levels of the CoCs nickel, copper, cobalt and arsenic as well as the additional metal confounders, mercury, lead and cadmium. Please see Appendix 11.4 for additional information regarding methodology, specimen type, specimen volume, specimen transport conditions, and reference values for each of the individual tests. All collection, storage, transport and analysis of samples will be carried out in strict accordance with applicable SOPs.

4.2.3.3 Non-Specimen related tests and data points

These tests and measures include lung function, skin sensitivity assessment, and additional general tests. All tests and measures will be carried out at the central study facility and supervised by trained study nurses. Lung function will be assessed by

spirometric tests including FVC, FEV1, and PEF. Skin sensitivity testing will be assessed using the thin-layer rapid-use epicutaneous (TRUE) test. This test is described in further detail in the section below. Finally, additional general measures will be carried out including ECG, blood pressure, and weight and height measurements.

4.2.3.3.1 Skin sensitivity assessment

Prior to dermatology testing, subjects will have filled out the health questionnaire which contains dermatology questions that will be used to obtain information concerning dermatological points of interest including questions about jewelry that pierces the skin and the possible presence of atopic dermatitis. A standardized ready to use patch test system, the TRUE test, will be employed (Brasch et al 2001; Suneja and Belsito 2001). This system has been found to be at least as comparable in terms of accuracy and reproducibility, to the conventional Finn Chamber technique of patch testing in its detection of nickel and cobalt allergic individuals (Suneja 2001, Golhausen 1989).

A group of trained study nurses will perform all patch test administration, including application and removal. Patch test scoring will be carried out by a smaller group of specially trained study nurses to maintain high inter-rater reliability. Patch tests will be applied on the upper back. Their edges will be marked with a hypoallergenic marker. Patch tests will remain on the skin for a period of 48 ± 2 hours. During this time, subjects will be given written instructions on test compliance (see Appendix 11.3 for more information). Following this, patch tests will be removed by a trained nurse. Skin sensitivity will be scored 48 hours following removal of the patch test (at 96 hours).

Patch test responses will be scored as either negative, or positive. A positive patch test result is interpreted as a 1+, 2+ or 3+ reaction. This interpretation is based on the following scale (ICDRG 1984): a) 1+ = diffuse confluent erythema with palpable infiltration; b) 2+ = erythema and infiltration with papules and discrete vesicles; and c) 3+ = spreading strong erythema and infiltration with coalescing vesicles/bullous reaction and / or crust with ulceration. Irritant reactions (weak, macular erythema without infiltration or a follicular (pore) pattern restricted to the area covered by the patch) are not regarded as positive and are denoted as “IR”.

4.2.4 Schedule of events

4.2.4.1 Overview

This section will describe the chronological flow of events experienced by a subject in this study. After being randomly selected as previously described, the potential subject will be contacted and asked to participate in the present study. A series of 3 visits at the central study facility will be scheduled for questionnaire and medical test administration, should the subject agree to participate in the study. In this event, a study participant will be given verbal study compliance instructions, they will be asked to pick up a 24-hour urine container at the central study facility and a study compliance instruction list will also be mailed to them (please see Appendix 11.3 for an outline of this information).

Subjects will then be required to attend their scheduled visits. These visits will take place over the course of 5 days. During the first visit (Day 1), study participants will complete and sign their informed consents/assent forms, complete the health questionnaire with the

assistance of a study nurse, donate blood and urine for the Medical Laboratory Screen and Metal Tests, and undergo cardiovascular, respiratory, dermatology, and general tests for the Non-Specimen Related Tests and Data Points. During this first visit the dermatology test will involve the application of a skin patch test. As such, a second (Day 3) and third visit (Day 5) will be required for removal of the patch test and scoring of the skin response, respectively. Specific procedures related to these tests will be discussed below.

4.2.4.2 Study visit 1 (Day 1)

4.2.4.2.1 Subject sign-In

The subject will arrive at the central test facility and be greeted by a study receptionist who will reference the subject's name against the appointment book, and collect the 24-hour urine sample. To confirm sobriety, the study participant will be given a breath alcohol test before proceeding. Any subject whose breath alcohol test exceeds the legal value of 0.08 will be disqualified. Subjects will then be assigned a Case Report Form (CFR) binder and be given a clipboard containing a Demographics Form to complete and Informed Consent Form to review. Adolescent subjects aged 12-17 years will be given an Adolescent Assent Form and their parents or guardian will be asked to review a Parental/Guardian Consent Form. Following this, the study participant will be greeted by a study nurse interviewer who will escort him/her into one of the four private interviewing stations. A parent or guardian may accompany adolescent subjects.

4.2.4.2.2 Interview administration

The interviewer will review the demographic information with the subject for completion and accuracy and validate it using a piece of photo I.D. supplied by the study participant. If the subject is an adolescent and does not have a piece of photo I.D., a birth certificate or a hospital card is acceptable. The nurse interviewer will confirm that the subject has complied with the parameters of the study over the past few days and then review the consent document(s) with the subject to ensure comprehension and answer any questions the subject may have. The interviewer will then have the subject sign and date both copies of the Informed Consent. The subject will be given one copy for his/her records. If the subject is an adolescent the parent/guardian will sign their consent form and the subject will sign their assent form. At this point, the subject will be ready for the health questionnaire interview. Parents or guardians will be asked to wait in the waiting room during the questionnaire administration so that adolescent subjects are given the utmost opportunity to answer freely.

4.2.4.2.3 Medical tests

Upon completion of the questionnaire, the interviewer will escort the subject into the first waiting room and place the Subject's CRF binder in the charting holder. If the study participant is an adolescent the parent/guardian may accompany them throughout the remainder of the visit for support.

The subject will be escorted into the first examination room in which all Non-Specimen Related Tests and Data Points will be assessed. The subject's height and weight will be

measured and their blood pressure will be assessed. Following this, a skilled professional will then administer a lung function test. This test will assess the following parameters: forced expiratory volume in 1 second (FEV1), forced vital capacity (FVC), and peak expiratory flow rate (PEFR). In addition, a breath carbon monoxide (CO) test will also be performed to assess recent smoking history. All measures will be recorded in the subjects CRF binder. Upon completion of this initial round of medical tests, the study participant will be escorted into the second waiting room and the Subject's CRF binder will be placed in the charting holder in that area.

The subject will then be escorted into a second examination room in which blood and urine specimens will be collected. These specimens will be necessary to carry out the tests specified for the General Medical Laboratory Screen and Metal Testing. In addition, patients will be given an ECG test during this time to examine cardiac function. All applicable information will be recorded in the Subjects CRF binder. Upon completion of the specimen collection and ECG testing, the subject will be escorted into the first waiting room and the subject's CRF binder will be placed in the charting holder in that area.

The subject will be escorted into a third examination room where a specially trained nurse will conduct dermatology testing. The nurse will first carefully review all information regarding the skin patch test with the subject and then apply the patch. Following this, the nurse will review the test compliance instructions with the study participant to ensure compliance. Finally, the nurse will review with the subject their

return visit schedule. All applicable information will be recorded in the Subjects CRF binder.

Upon completion of the application of the dermatology patch, the Subject will be escorted to the sign out waiting area. Subjects will be signed out following a review of the CRF binder by the study nurse and confirmation that the subject completed all components of Visit 1, understood the dermatology patch compliance instructions, and understood when he/she must return for Visit 2 and Visit 3. If the subject is an adolescent, and if the parent/guardian has not been present throughout the specimen and data points collection, the parent/guardian must be present at the time of sign out to ensure an understanding of the above.

4.2.4.3 Study visit 2 (Day 3)

The study participant will return for their second scheduled appointment on day 3 and be greeted by the receptionist who will reference the subjects name against the appointment book. The receptionist will locate the subject's CRF binder and ensure the subjects identity. The subject is escorted to the first waiting room where the subject's CRF binder is placed in the charting holder.

The subject will then be escorted into an examination room. There, a trained study nurse will remove the patch. If the subject is an adolescent the parent or guardian may accompany them during this procedure.

Upon having the patch removed, the subject will be escorted back into the reception waiting room where the sign out nurse will review the subject's CRF binder and ensure that the subject has completed all components of visit 2 and understood when he/she must return for visit 3. If the subject is an adolescent, the parent or guardian must be present at the time of sign out to ensure an understanding of the above.

4.2.4.4 Study visit 3 (Day 5)

The study participant will return for their third scheduled appointment on day 5. The receptionist will again greet the subject and reference the subject's name against the appointment book, locate the subject's CRF binder, and ensure the subject's identity. The subject is escorted to the first waiting room where their CRF binder is placed in the charting holder.

The subject will be escorted into an examination room where a trained nurse will score the skin reaction to the patch. If the subject is an adolescent the parent or guardian may accompany them for the dermatology patch scoring.

Upon having the patch scored, the subject will be escorted back into the reception waiting room where the sign out nurse will review the subject's CRF binder and ensure that all they successfully completed visit 3, understood that following the completion of the study a final report indicating their test results will be held for them at the facility for pick up. If the subject is an adolescent, the parent or guardian must be present at the time of sign out to ensure an understanding of the above. The subject will then be given a payment of

\$35 for completion of the study. This amount was determined based on transportation costs during the study, four return trips to and from the study facility.

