3.2.2.5 Validation

The individual medical tests described above have been included both for their utility in measuring general health and health conditions associated with exposure to the CoCs, as well as for purposes of validation. That is, specific medical tests also can be used as objective measures to validate reported medical health information from the health

questionnaire that is subjective in nature (Moffat et al., 2000; Smith- Sivertsen et al., 2000).

Medical tests that will serve as validators in this study include:

- Bilirubin test: validates the jaundice question in the questionnaire,
- Plasma cotinine test: validates recent smoking history question in the questionnaire,
- Serum TSH and fT4 test: validates thyroid condition questions in untreated individuals,
- ECG test: validates history of heart attack question in the health questionnaire,
- CO breath test: validates recent smoking history question in the health questionnaire,
- FEV1/FVC/PEFR tests: help to validate chronic bronchitis, emphysema, chronic obstructive pulmonary disease, asthma and other respiratory questions from the health questionnaire, and
- Skin patch tests: validates contact dermatitis question from the health questionnaire.

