5.0 Data Management

5.1 Data collection and quality control

All data, including the signed informed consent (Adult Consent, Adolescent Assent, Parental or Guardian Consent) will be collected on a two-part NCR document. The informed consent will be provided as a single document for adult consent, parental or guardian consent or adolescent assent. Once written consent has been given, a copy will be retained by the subject, and one by Ventana. The informed consent will be provided with a unique code and inserted into a case report form (CRF) for the study participant. The CRF will be two-part NCR. The top page (white sheet) will be classed as the original document and the second page (yellow sheet) will be classed as the file copy.

At the completion of each questionnaire, the interviewer coordinator will review for completeness. Alongside questions that have not been answered by the study subject, the interviewer will sign their initials. At the bottom of each page, the interviewer will sign

their initials. Each white page will be removed from the CRF upon completion and submitted for data entry.

All data provided on test samples from the laboratory will be provided in electronic format predetermined for compatibility with the central data base. A common unique code will be utilized for each participant.

Data collection by the central laboratory will be done via electronic data capture.

Data from the health test machines will be provided from a print-out that will be used for double entry methodology.

Data from the ECG will be entered into the central data base as descriptive text.

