 - ___ Trades certificate or diploma from a vocational school or apprenticeship training
 - ___ Non-university certificate or diploma from a community college, CEGEP, school of nursing, etc.
 - ___ University certificate below bachelor's level
 - ___ Bachelor's degree
 - ___ University certificate or diploma above bachelor's degree

10. Can you estimate in which of the following groups your household income falls? 

ADULT

Was the total household income ...

- Less than \$20, 000?
 - Less than \$10, 000?
 - Less than \$5, 000?
 - \$5, 000 or more?
 - \$10, 000 or more?
 - Less than \$15, 000?
 - \$15, 000 or more?
- \$20, 000 or more?
 - Less than \$40, 000?
 - Less than \$30, 000?
 - \$30, 000 or more?
 - \$40, 000 or more?
 - Less than \$50, 000?
 - \$50, 000 to less than \$60, 000?
 - \$60, 000 to less than \$80,000?
 - \$80, 000 or more?
- No Income

Residential Information

11. Please fill in the following table for your current and all past residences in Port Colborne.

Address ¹	Period of Stay ²		Type of Dwelling ³	Age of Residence ⁴
	From	To		

¹Please indicate street address, city, province, country, and postal code.

²Please indicate from MM/YYYY to MM/YYYY.

³Please indicate one of the following:

- Single Detached House
- Semi-Detached or Double (side-by-side)
- Garden House, Town-House or Row House
- Duplex (one above the other)
- Low-rise apartment (less than 5 stories)
- High-rise apartment (5 or more stories)
- Institution
- Collective dwelling (such as a Hotel/Motel, Rooming or Boarding House)
- Mobile home
- Farm or Acreage
- Other (please specify _____)

⁴Please indicate number of years.

12. If you have resided or are residing in more than one home concurrently, please fill in the following table: CHILD

Address	Percentage of Time Spent
#1	
#2	

Occupational Information

13. a) Do you now or have you ever worked in one of the following industries/occupations: Y/N ADULT.

b) If yes, please specify which industry/occupation:

- | | |
|--------------------------------|-----------------------------------|
| 1 - Underground mining | 8 - Welding |
| 2 - Smelting | 9 - Brazing |
| 3 - Metal Refining | 10 - Sintering |
| 4 - Foundry work | 11 - Plumbing |
| 5 - Steelmaking | 12 - Metal plating/electroplating |
| 6 - Metal Cutting and grinding | 13 - Shipbuilding/breaking |
| 7 - Boiler maker/repairer | 14 - Lumberyard/Sawmill |

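### The protocol does not mask patch-test scorers to residence or questionnaire answers, and it brings the participant's CRF binder to the scoring visit

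*Protocol*

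**What the plan says.** **Handling of the binder.** Sections 4.2.4.2.1 to 4.2.4.4 describe one CRF binder per participant. It is assigned at sign-in, follows the participant from the interview through the examination rooms, and is retrieved at Visits 2 and 3. At Visit 3: "The subject is escorted to the first waiting room where their CRF binder is placed in the charting holder". Next, "a trained nurse will score the skin reaction to the patch".

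**Pages in the CRF.** Section 5.1 describes a two-part form. "Each white page will be removed from the CRF upon completion and submitted for data entry". The yellow sheet is a file copy, and its storage place is not given. The consent form is also inserted in the CRF.

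**Order of events.** Section 4.2.3.3.1 states that before dermatology testing "subjects will have filled out the health questionnaire which contains dermatology questions". The questionnaire (Appendix 10.1) includes a residence table, introduced by "Please fill in the following table for your current and all past residences in Port Colborne" (Q11). It also has jewellery items (Q37–39) and, in the medical section, skin-condition items (Q20–22).

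**The reading.** The lowest positive grade is "a) 1+ = diffuse confluent erythema with palpable infiltration". Weak redness without infiltration, or a follicular pattern confined to the patch area, is coded as irritant and not positive. The safeguard on scorers is: "Patch test scoring will be carried out by a smaller group of specially trained study nurses to maintain high inter-rater reliability".

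**Use of the result.** Section 6.2.1.2 defines exposure by residence, with the Rodney Street area (Area 3) as exposed and everywhere else as non-exposed. Section 6.4 singles out that contrast, and mock Tables 8 and 11 include the nickel and cobalt patch results in it. Section 3.2.2.5 adds: "Skin patch tests: validates contact dermatitis question from the health questionnaire".

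**The concern.** The boundary between 1+ and an irritant reaction is settled by looking and touching. A scorer who knows where the participant lives, or what was answered about dermatitis and piercings, may resolve borderline sites differently. If that knowledge tracks area, the error is differential, and no adjustment for age, sex or other covariates removes it.

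The validation has a related weakness. Section 3.2.2.5 presents the medical tests as objective checks on subjective self-report. A reading made with the self-report in view is not an independent check.

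Using a small, specially trained scoring group improves agreement between scorers. It does not guard against a tendency that the scorers share.

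**Working it through.** **1. What the sections establish together**

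| Question | Protocol | Status |
|---|---|---|
| Is the binder at the scoring visit? | Section 4.2.4.4 | Stated |
| Are white pages gone by then? | Sections 5.1 and 5.4: removed on completion; originals leave the site daily | Stated |
| Are yellow questionnaire pages in the binder on Day 5? | Section 5.1 calls them a file copy, with no location | Not stated; possible |
| Does the scorer read them? | Not described. The sign-out nurse reviews the binder after scoring | Not stated |
| Is address kept apart as identifying information? | Appendix 10.1 says identifying information is held separately, but Section 4.2.2.1 names only name and date of birth as identifying | Unclear |
| Is the scorer masked to residence or answers? | No section says so | Absent |

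The documents therefore show a missing safeguard and a plausible route to unmasking. They do not show that unmasking will occur.

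**2. The plan's own figure for this endpoint**

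Section 6.1.1 gives 234 women in the Rodney Street area, 251 elsewhere, an anticipated prevalence of 9.5%, 80% power and 5% type I error, with a detectable odds ratio of 2.2. Sidedness is not stated; two-sided is assumed here. Solving the two-proportion sample-size formula with continuity correction gives 2.20, which agrees. Without the correction it gives 2.13. Masking the scorer changes neither the sample size nor this figure.

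**3. Illustration of the size of bias**

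Assume no true difference (9.5% in both groups), and that a share *f* of non-reactors is over-read as positive in Area 3 only. The protocol gives no value for *f*.

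- Apparent prevalence: p₁ = 0.095 + *f* × 0.905
- Spurious odds ratio: [p₁ / (1 − p₁)] / [0.095 / 0.905], with 0.095 / 0.905 = 0.1050
- Chance of a significant result: two-sided 5% test of two proportions, 234 against 251, with pooled standard error for the critical value and unpooled standard error for the distribution of the difference
- Women over-read: 234 × 0.905 = 211.8 non-reactors, times *f*

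| *f* (assumed) | Women over-read | p₁ | Odds ratio | Chance of p < 0.05 |
|---|---|---|---|---|
| 0 | 0 | 9.5% | 1.00 | 5.0% |
| 1% | 2.1 | 10.4% | 1.11 | 6.3% |
| 2% | 4.2 | 11.3% | 1.21 | 10.1% |
| 3% | 6.4 | 12.2% | 1.33 | 16.2% |
| 5% | 10.6 | 14.0% | 1.55 | 34.2% |

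For *f* = 5%: p₁ = 0.095 + 0.04525 = 0.1403; odds 0.1403 / 0.8597 = 0.1631; 0.1631 / 0.1050 = 1.55.

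**The case against.** The strongest reply is that the protocol never says the Day 5 binder contains the questionnaire, or that the scorer opens it. White pages are gone, the yellow copy may be filed elsewhere, and the binder waits in a charting holder. An address is also not an area code. Area 3 is a set of street boundaries (Section 4.1.2), no section puts a stratum code in the CRF, and no staff come from Port Colborne (Section 4.2.2.2.1). Scoring has a small trained group, a graded scale and an explicit irritant category. The misreading rates are invented, act in one direction only, and at 1% do little harm.

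Most of this stands as a limit on the point. It does not supply the missing safeguard: the sections cited concern confidentiality and reliability, and none of them masks the scorer. The dermatitis and jewellery answers, unlike an address, need no local knowledge to interpret.

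A reader might infer three stronger things that the documents do not support:

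- *Scorers work from the participant's address and answers.* This is an inference about where the yellow copies are kept.
- *The whole Area 3 comparison is compromised.* Blood, urine, metal and breath carbon monoxide results are laboratory or instrument readings, which the patch scorer cannot influence.
- *The questionnaire should be reordered to mask interviewers.* Interviewers first check the demographic form against photo identification (Section 4.2.4.2.2), and respondents know where they live, so moving the residence table would not achieve masking.

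**Conclusion.** The point holds for the patch-test scorer only. The protocol specifies no masking to residence or questionnaire answers for a reading that depends on judgement. It brings the binder to the scoring visit without saying that the copies of those answers are elsewhere. The patch-test rows of Tables 8 and 11 and the validation in Section 3.2.2.5 are exposed to an avoidable bias.

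Its size cannot be determined from the protocol. Under assumed over-reading of 1% to 5% of Area 3 non-reactors, with no true difference, the spurious odds ratio is about 1.11 to 1.55 and the false-positive rate among the planned women is about 6% to 34%. At the low end this is negligible. At the high end it is material, though still below the plan's detectable odds ratio of 2.2. The case for acting rests on the low cost of prevention and on the fact that analysis cannot correct such an error afterwards.

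**What to change.** Amend Sections 4.2.3.3.1 and 4.2.4.4 to state that scorers are masked to residence and questionnaire answers. The scorer records the result on a one-page sheet bearing only the participant's existing unique code. Questionnaire, demographic and consent pages, including yellow copies, stay out of the binder at Visit 3 until the score is recorded. Section 5.1 should say where the yellow copies are held in the meantime.

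The cost is one extra page per participant and slightly more paper handling at Visit 3. Staffing, sample size, question wording and questionnaire order are unchanged.
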